To increase the chance that we engage participants, during an initial 7-day period, participants will be offered access to the study smartphone app and incentives. We have used similar induction procedures in our prior studies to successfully engage participants. Participants will have the smartphone app installed on their smartphones and will be taught how to use the app. Participants will then be asked to use the application to record a video of themselves for 7 days. Each video will be uploaded into a web portal, which can be securely accessed by our research staff, and will be reviewed by our research staff. Participants will be able to earn \$10 per day over the 7-day period for submitting a video of themselves each day. Participants who use the smartphone application to record and submit videos on 6 or more days during the 7-day induction period will be randomly assigned to a study group (as described in detail below).

Experimental Design

Participants (N=375) will be randomly assigned to one of two Contingency Management groups—a Buprenorphine Adherence and Opiate Abstinence group and a Buprenorphine Adherence Only group—or a Usual Care (Control) group. A computerized urn randomization procedure will be used to randomize participants and to balance groups on three characteristics that may influence outcome: (1) opioid use severity (used illicit opioids ≥ 15 days out of the past 30 days, Y/N), (2) cocaine use (cocaine-positive urine, Y/N), and (3) age (greater than rolling median, Y/N). Participants will be stratified by opioid use, cocaine use, and age because each has been associated with buprenorphine treatment outcomes.⁶⁵⁻⁶⁷ Participants will be assessed every month during the 3-month intervention and every 3 months during a 9-month follow-up period. We will teach participants the details of their study group with instructions and quizzes.

General Contingency Management Procedures

Both Contingency Management groups (Buprenorphine Adherence and Opiate Abstinence and Buprenorphine Adherence Only participants) will receive incentives for daily buprenorphine use. Buprenorphine Adherence and Opiate Abstinence participants also will receive incentives for providing opiate-negative saliva samples. Both of the Contingency Management interventions will have the following

Date: April 12, 2023

Principal Investigator: [name]

Application Number: IRB00220692

features:

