Assessments will be conducted at intake, every month during the 3-month intervention period, and at 6, 9, and 12 months after randomization. Participants will be paid \$50 for completing each of the intake and monthly assessments, and \$100 for completing the follow-up assessments. These assessments will be collected using REDCap. Whenever possible, assessments will be conducted remotely via phone or web-conferencing.

Intake Only Assessment Instruments

DSM-5 Checklist for Opioid Use Disorder. The DSM-5 checklist for opioid use disorder is a structured assessment that will be used to determine if participants have opioid use disorder.

Non-Study Medical and Other Services – NSMOS-BL. This assessment will be used to collect information on medical services participants may have received in the 3 months prior to study intake.

Intake and Major Assessment Instruments

Urine and saliva toxicology testing. Urine and saliva samples will be collected and tested for opioids and other drugs. Toxicology testing may be conducted by sending a testing kit to participants through the mail. Participants would then be asked to complete the toxicology tests (urine and saliva) and provide a video showing the results of the tests using the study smartphone app.

Time-line follow-back (TLFB). Participants will be asked whether or not they are in treatment for their opioid use disorder, including treatment other than buprenorphine (e.g., methadone maintenance). For participants who report being in buprenorphine treatment, the TLFB procedure will be used to elicit participants' self-reported taking of their buprenorphine dose each day. Pharmacy and/or clinic records (with participant permission) may be used to confirm self-reported data.

Opioid Overdose Risk Assessment. An opioid overdose risk assessment will be used to assess the rate at which participants report engaging in behaviors that may put them at risk for an opioid overdose.

The Addiction Severity Index – Lite (ASI-Lite). The ASI-Lite is a structured interview designed to assess problem severity in areas commonly affected by drug and alcohol use (medical, legal, employment, family/social, and psychiatric) with good reliability and validity.

Smartphone Form. This questionnaire will document participants' access to and willingness to use a smartphone during the study.

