We will analyze measures assessed repeatedly over time with a longitudinal logistic regression model. Within-person correlated outcomes will be handled using generalized estimating equations (GEE; Zeger, Liang, & Albert, 1988). Measures assessed once will be analyzed using logistic regression. The magnitude of effects will be expressed using odds ratios with 95% confidence intervals. Retention in buprenorphine treatment during the intervention period will be analyzed with a Cox proportional hazards model. We will adjust the intent-to-treat analyses for covariates used for stratification (Pocock, Assmann, Enos, & Kasten, 2002).

Primary outcome analyses. We will fit a longitudinal logistic regression model $\text{logit}(Y_{ij}) = \beta_0 + \beta_1 tx_1 + \beta_2 tx_2 + \beta_3 x_{2-4} + \varepsilon_{ij}$, where Y_{ij} is evidence of buprenorphine adherence or opiate abstinence for the i th person at the j th timepoint (3 visits over 12 weeks), β_1 is the covariate of interest representing the expected increase in log odds of evidence of buprenorphine adherence or opiate abstinence as a function of assignment to the treatment group, and β_{2-4} are the coefficients for the 3 randomization covariates. We also will fit models with time and time by treatment interactions to look at change over time in buprenorphine adherence and opiate abstinence in each study group.

Secondary outcome analyses. We will fit longitudinal logistic regression models for the secondary measures. We will assess effects during the 3 months by fitting analogous models as described above for each outcome, including fitting models to look at change over time in each study group. Retention in buprenorphine treatment will be analyzed using a Cox proportional hazards model.

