Missing data. We expect to collect $\geq 85\%$ of the study assessments. Our primary approach to handle missing data will be to impute missing values as the adverse outcome (e.g., buprenorphine-negative urine sample). Model parameter estimates from this approach will be compared to a method without imputation. If these methods yield differing results, conclusions will need to be tentative, but results from both approaches will be reported in publications. To investigate sensitivity to missing values, participants with and without missing values will be compared by covariates and group assignment. If rates are higher than expected, we may use mixed effects models rather than GEE estimation, as the former has less strict assumptions regarding missing data (missing at random, rather than missing completely at random).

Power Analyses

We used Liu and Liang⁸⁴ to determine the number of participants required to detect a difference of 15% between groups using the three monthly assessments during the 3-month intervention period with 80% power and adjusting for missing data (15% missing). Based on these analyses, we will randomize a total of 375 participants (125 per group).

Buprenorphine adherence. We expect a fairly large difference in buprenorphine adherence between the two Contingency Management groups and the Usual Care group. Specifically, we expect that each Contingency Management group will provide urine samples positive for buprenorphine on 85% of the assessments, whereas we expect that the Usual Care group will provide urine samples positive for buprenorphine on 45% of the assessments. Thus, we expect to obtain a 40% difference in buprenorphine adherence between each of the Contingency Management groups and the Usual Care group.

Opiate abstinence. We expect large differences in opiate abstinence between each of the two Contingency Management groups and the Usual Care group, but a relatively small difference in opiate abstinence between the two Contingency Management groups. The Power Analysis was designed to allow

Date: April 12, 2023

Principal Investigator: [name]

Application Number: IRB00220692

us to detect the smallest difference in opiate abstinence between groups: the difference between the Buprenorphine Adherence Only (expected 68% opiate negative) and the Buprenorphine Adherence and Opiate Abstinence (expected 83% opiate negative) groups; to detect this difference, we would need 106 participants.

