Total sample size. Based on the analyses described above, we would need 106 participants per group to detect effects between the pairs of groups for the planned comparisons. After adjusting for the anticipated rates of missing data (15% missing), we need to randomize 125 participants to each of the three groups to ensure that we have sufficient sample sizes (125 participants x 0.85 collected assessments = 106 participants per group). Thus, we will randomize a total of 375 participants.

d. Early stopping rules.

The study investigators and a Data Monitoring Committee (DMC) will provide data and safety monitoring of the proposed trial. To monitor adverse events, all staff members who have regular contact with study participants are instructed on the need to report to an investigator any indication that an adverse event has occurred. When the staff members and investigators learn of an adverse event, they will investigate until they have determined as many of the relevant details of the adverse event as possible. To provide consistent monitoring of adverse events across groups, participants will be asked about all categories of adverse events at each routine assessment visit conducted throughout the study. At least one investigator will review each adverse event as it occurs. The DMC will review a summary of adverse events annually. This frequency of review will be increased if the adverse events occur at a higher rate than anticipated. The protocol can be stopped based on recommendations of the investigators or DMC who are reviewing the adverse events in the study. We will ask the investigators and DMC to recommend that the trial be stopped if a review of the adverse events suggests to any of the investigators or DMC members that the number of related adverse events is unacceptably high. The investigators or DMC will be allowed to request statistical analyses to compare the groups on the rates of different adverse events or to have the adverse event data summarized in other ways that they deem appropriate.

8. Risks

a. Medical risks, listing all procedures, their major and minor risks and expected frequency.

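### The opiate-abstinence model leaves out the intake opiate urine result, which is already collected, and so gives up some power on the contrast that sized the trial

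*Combined protocol and SAP*

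**What the plan says.** Section 7c (Statistical Analyses) gives the primary model for both outcomes as a logistic GEE over three monthly visits. It has two treatment terms and further terms that "are the coefficients for the 3 randomization covariates". The general rule there is the same: "We will adjust the intent-to-treat analyses for covariates used for stratification".

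Those covariates are named in section 4a (Experimental Design). They are illicit opioid use on at least 15 of the past 30 days, "cocaine use (cocaine-positive urine, Y/N"), and age above the rolling median. One of the three is therefore a urine result available before assignment.

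Urine toxicology is listed in section 4a under the instruments used at both intake and the major assessments: "Urine and saliva samples will be collected and tested for opioids and other drugs". No section puts the intake opiate result into the abstinence model.

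In section 7c (Power Analyses), the sample size was chosen to allow "us to detect the smallest difference in opiate abstinence between groups", with 68% and 83% opiate-negative expected in the two Contingency Management groups. The primary missing-data rule is stated as "Our primary approach to handle missing data will be to impute missing values as the adverse outcome".

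**The concern.** The abstinence outcome is a yes/no opiate-negative urine at each monthly visit. The same test at intake is that outcome's baseline value and is usually among the stronger predictors available. The plan adjusts for the intake cocaine urine but not for the intake opiate urine. The nearest term in the model is a dichotomised count of use days.

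What is at stake is power on one comparison. The contrast between the two Contingency Management groups was sized at 80% with no margin, and the missing-equals-adverse rule shrinks the difference it must detect. A covariate already in the database is the cheapest way to recover some of that loss. Buprenorphine adherence, expected at 45% versus 85%, has power near 100% with or without a baseline term.

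**Working it through.** **Inputs from the documents.** 68% versus 83% opiate-negative; three visits; 80% power; 15% missing, counted as adverse; 106 per group needed and 125 randomized; three randomization covariates.

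**Inputs assumed.** Two-sided alpha 0.05 (not stated, but in line with the planned 95% intervals); exchangeable visit correlation ρ; intake prevalence; and all correlations involving intake status or the severity covariate.

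**1. The plan's own figure.** A single time point needs 127.9 per group (pooled test), 125.1 (unpooled) or 132.5 (Wald test on the log odds ratio). Three exchangeable visits multiply this by (1 + 2ρ)/3. On the log-odds scale, 132.5 × (1 + 2 × 0.70)/3 = 106.0. The unpooled figure gives 106 at ρ of about 0.77 and the pooled figure at about 0.74. So 106 fits ρ of 0.70 to 0.77. This is a back-solve, since ρ is not given. The inflation step reproduces: 106/0.85 = 124.7, rounded to 125, which matches "125 participants x 0.85 collected assessments = 106 participants per group".

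**2. Starting power under the planned missing-data rule.** The expected proportions become 0.85 × 68% = 57.8% and 0.85 × 83% = 70.55%, a difference of 12.75 points. Take ρ = 0.70 and 125 per group, and let the variance of a participant's three-visit mean be (v + 2c)/3, where v is the visit variance and c the between-visit covariance after imputation.

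| Pattern of missingness | Variance, lower arm | Variance, upper arm | SE of difference | z | Power |
|---|---|---|---|---|---|
| Single visits | 0.1547 | 0.1168 | 0.0466 | 2.74 | 78.1% |
| Whole participants | 0.2069 | 0.1838 | 0.0559 | 2.28 | 62.6% |

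These figures carry no covariate adjustment. They set the level from which the gain is measured.

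**3. Adding the intake result, by simulation.** Logistic GEE with robust SE, 6,000 replicates per setting, 125 per group, ρ = 0.70, 50% opiate-negative at intake. The severity indicator (30% high; correlation −0.3 with intake-negative and −0.2 with outcome, the latter set to 0 in the zero-correlation row) is in both models.

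| Intake-to-visit correlation | Single visits missing: without → with | Whole participants missing: without → with |
|---|---|---|
| 0 | 77.5% → 77.4% | not run in this set |
| 0.2 | 78.9% → 79.9% | 62.3% → 62.7% |
| 0.3 | 79.2% → 81.6% | 62.4% → 63.6% |
| 0.4 | 79.0% → 84.2% | 62.4% → 65.9% |

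The Monte Carlo SE of each paired gain is 0.14 to 0.39 points. Separate code with 3,000 replicates gave gains of 0, 0.9, 2.0 and 6.0 points (single visits) and 0, 0.3, 2.1 and 3.5 points (whole participants) at 0, 0.2, 0.3 and 0.4. With 60% or 70% opiate-negative at intake and single visits missing, the gain was 0.7 to 5.3 points. A correlation of 0.5 was not used: with 50% at intake and 83% at follow-up the maximum is √(0.17/0.83) = 0.45.

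**4. Where the gain appears.** The standardised risk difference is 12.7 points in both models. With single visits missing, its empirical SD falls from 4.60 to 4.56, 4.59 to 4.48 and 4.62 to 4.32 points at 0.2, 0.3 and 0.4. The squared ratios are 1.018, 1.050 and 1.144, or about 2%, 5% and 14% more effective sample size. The SE of the log odds ratio does not fall (0.209 to 0.211 at 0.3); the conditional odds ratio moves from 1.78 to 1.82.

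**5. Validity.** Simulated type I error at 68% versus 68%, without and with the intake term, was 5.1% and 5.1% at correlation 0.2, and 4.9% and 5.1% at 0.4.

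**The case against.** The strongest case is that this is a preference, not a fault. The model is pre-specified, adjusts for its stratification factors and is valid under randomization. That stands, and the point is put only as an efficiency gain.

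The severity covariate already measures recent opioid use, so it may carry much of what the intake urine would add. This reduces the gain. A variance check shows by how much, starting from 80% power and 106 per group with visit correlation 0.75, no imputation, and a factor of 1 minus the squared partial correlation of intake status with the participant mean given severity:

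- Severity correlated 0.3 with intake and 0.2 with outcome: at an intake-to-visit correlation of 0.3 the squared partial correlation is 0.080. Power becomes 83.2%, or 106 × 0.920 = 97.5, so 98 per group for equal power.
- Severity correlated 0.5 and 0.3: the squared partial correlations are 0.0045, 0.040 and 0.112, and the gains are 0.2, 1.6 and 4.5 points at 0.2, 0.3 and 0.4.

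Eligibility requires buprenorphine treatment but no opiate-positive urine, so intake results could be nearly all one value. The gain would then be close to zero, and no simulation covered that case with a non-zero correlation.

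The stated primary aim is Contingency Management against Usual Care, where large differences are expected. The documents give no Usual Care opiate-negative rate. At an assumed 48% or 43% against 68% (106 per group, ρ = 0.74, no imputation), power is already about 91% or 99%, so that aim would gain little. The gain matters for the planned comparison between the two Contingency Management groups.

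Finally, the fall to about 62% power under whole-participant missingness is a missing-data problem. The intake term recovers only 0.4 to 3.5 points of it.

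**Conclusion.** The concern holds as an inexpensive improvement that the plan should adopt. The intake opiate result exists, is not used in the abstinence model, and bears on the contrast that fixed the sample size. A reasonable expectation is a gain of about 0 to 5 points of power. It is nil if intake status does not predict follow-up, and smaller where severity overlaps with it or whole participants are lost.

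The direction is secure if intake status is prognostic beyond the severity covariate. The size is not, because intake prevalence and every correlation with intake status are assumed and the visit correlation is back-solved. Confidence in the magnitude is therefore medium.

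**What to change.** Before any by-group outcome data are examined, add to section 7c:

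> The opiate-abstinence model will include the intake opiate urine result (negative/positive) in addition to the three randomization covariates. The treatment effect will be reported as the conditional odds ratio and as a standardised marginal risk difference, each with a 95% CI.

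Two details should be settled in the same edit. First, state whether the intake result is classified by the rule in section 7a, including its treatment of buprenorphine and methadone. Second, state how a missing or invalid intake result is handled, for example with a separate category so that no randomized participant is dropped. Matching intake values may be added to the adherence and repeated secondary models for consistency, with little gain expected for adherence.

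The cost is wording and one additional effect measure with its variance method; no new data are needed. The odds ratio becomes conditional on one more covariate and moves slightly away from 1, which is why the risk difference should stand beside it. If intake status proves not to be prognostic, almost nothing is lost.

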c. Blinding, including justification for blinding or not blinding the trial, if applicable.

Participants will not be blinded as to their study condition because participants in the incentive intervention cannot be blind to that intervention.

d. Justification of why participants will not receive routine care or will have current therapy stopped.

N/A

e. Justification for inclusion of a placebo or non-treatment group.

N/A

f. Definition of treatment failure or participant removal criteria.

Participants will be removed from the study if they threaten the safety of staff or other research participants, or of any other persons on the Johns Hopkins Bayview Campus.

g. Description of what happens to participants receiving therapy when study ends or if a participant's participation in the study ends prematurely.

Throughout the study, participants will be given referrals to services they might need (e.g., drug counseling, housing, medical, or employment services). Participants will continue to receive buprenorphine treatment as long as that treatment is available in the program they attend.

5. Inclusion/Exclusion Criteria

Applicants will be invited to participate in this study if they: a) are \geq 18 years old, b) meet DSM-5 criteria for opioid use disorder, c) are enrolled in buprenorphine treatment, and d) use the smartphone

Date: April 12, 2023

Principal Investigator: [name]

Application Number: IRB00220692

application to record and submit videos on 6 or more days during the 7-day induction period. Applicants will be excluded if they: a) have current suicidal/homicidal ideation, or b) are unwilling or unable to use a smartphone.

6. Drugs/ Substances/ Devices

a. The rationale for choosing the drug and dose or for choosing the device to be used.

N/A

b. Justification and safety information if FDA approved drugs will be administered for non-FDA approved indications or if doses or routes of administration or participant populations are changed.

N/A

c. Justification and safety information if non-FDA approved drugs without an IND will be administered.

N/A

7. Study Statistics

We will compare the three study groups on primary and secondary outcome measures.

a. Primary outcome variable.

Buprenorphine Adherence. We will assess the percentage of participants with buprenorphine-positive urine samples at the monthly assessments during the 3-month intervention evaluation period (Yes/No at each assessment).

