Opiate Abstinence. We will assess the percentage of participants with opiate-negative urine samples (excluding buprenorphine and methadone if self-report confirms that the participant is enrolled in buprenorphine or methadone treatment) at the monthly assessments during the 3-month intervention evaluation period (Yes/No at each assessment).

b. Secondary outcome variables.

Buprenorphine Diversion. We will assess the number of days participants report diverting their daily buprenorphine dose (selling or giving their buprenorphine dose to someone else) during the 28 days prior to each of the monthly assessments during the 3-month intervention evaluation period (based on TLFB).

Retention in Buprenorphine Treatment. We will assess the last day that participants reported taking buprenorphine during the 3-month intervention evaluation period (based on TLFB).

Overdose risk. We will assess the rates at which participants report engaging in overdose risk behaviors at the monthly assessments during the 3-month intervention evaluation period (based on total scores from the opioid overdose risk assessment).

Psychosocial Functioning. We will assess patient-reported psychosocial functioning during the 3-month intervention evaluation period (based on the ASI-Lite).

Quality of Life. We will assess patient-reported quality of life during the 3-month intervention evaluation period (based on scores from the SF-36).

Patient Treatment Satisfaction. We will assess patient-reported treatment satisfaction during the 3-month intervention evaluation period (based on scores on the CSQ-8).

Post-Intervention Effects. We will assess the outcomes described above every 3 months during a 9-

Date: April 12, 2023

Principal Investigator: [name]

Application Number: IRB00220692

month follow-up after the intervention ends.

c. Statistical plan including sample size justification and interim data analysis.

Statistical Analyses

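### Secondary outcomes defined as scores or a day count are assigned the yes/no logistic model, with no cut-point, no grouped or ordinal form, and no stated adverse value when data are missing

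*Combined protocol and SAP*

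**What the plan says.** Section 7c (Statistical Analyses) gives one model for anything measured repeatedly, a longitudinal logistic regression fitted by GEE. For single measurements: "Measures assessed once will be analyzed using logistic regression". For effect size: "The magnitude of effects will be expressed using odds ratios with 95% confidence intervals". Under Secondary outcome analyses it adds: "We will fit longitudinal logistic regression models for the secondary measures", to be done by "fitting analogous models as described above for each outcome". The only exception is retention, which has a Cox model.

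The model described above is the primary one. Section 7a marks both primary urine outcomes as "Yes/No at each assessment".

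Section 7b gives no secondary outcome that label:
- Diversion: "We will assess the number of days participants report diverting their daily buprenorphine dose", counted over the 28 days before each monthly assessment.
- Overdose risk: described as rates of risk behaviours, but "based on total scores from the opioid overdose risk assessment".
- Quality of life and treatment satisfaction: scores from the SF-36 and the CSQ-8.
- Psychosocial functioning: the ASI-Lite is named as the source, and nothing more.

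Under Missing data, the primary approach sets missing values to the adverse outcome. The only example is a urine result, and the rule is not confined to the urine outcomes. A comparison without imputation is planned, and mixed models may replace GEE if more data are missing than expected.

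**The concern.** A model analogous to the primary one needs a 0/1 response. Four secondary outcomes are defined as a count or a score, and a fifth is not defined beyond its instrument. To run the stated analysis, someone must supply a cut-point or a different form of logistic model, and the plan supplies neither. For the SF-36 and ASI-Lite, the variable must be chosen as well. The imputed value is open in the same way, because adverse has an obvious meaning for a urine test but not for a day count or a score.

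Secondary aims a (diversion), c (its overdose-risk part), d (functioning and quality of life) and e (satisfaction) are affected, and so is aim f where these outcomes are followed after the intervention. Variable, cut-point, model form and imputed value could all be settled after results are visible. The most obvious workaround, splitting a score in two, also discards information.

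**Working it through.** No figure in the plan depends on this point, so there is none to reproduce. The first step is a comparison of text; the other two are illustrations on assumed values.

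**Step 1. Definitions against the assigned model.**

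| Outcome | Type in 7a/7b | Model in 7c | Fits as written? |
|---|---|---|---|
| Two urine outcomes (primary) | Yes/no | Logistic GEE | Yes |
| Diversion | Days, 0 to 28 | Same | No: an any/none split or a days-out-of-28 binomial would be needed; neither is stated |
| Overdose risk | Total score | Same | No: no cut-point or ordinal form |
| Quality of life | SF-36 scores, which one not named | Same | No |
| Satisfaction | CSQ-8 scores | Same | No |
| Psychosocial functioning | Instrument only; 4a lists five problem areas and 7b selects none | Same | Cannot be judged |
| Retention | Last reported day of use | Cox | Outside this point |

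A standard binary logistic routine rejects a 0-to-28 count, because the response must lie between 0 and 1.

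**Step 2. Cost of splitting a score at the median.** Assumptions, none from the plan: normal score with SD 1 and common correlation ρ = 0.7 between visits and with intake. The three monthly visits are from the plan.

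- Variance of a person's mean score: (1 + 2ρ)/3 = 2.4/3 = 0.800.
- Correlation after the split: (2/π) arcsin(0.7) = 0.494. Variance of the mean proportion: 0.25 × (1 + 2 × 0.494)/3 = 0.1656.
- A small shift in the score moves the proportion by 0.3989 times that shift, and 0.3989² = 0.159. Information kept: 0.159 × 0.800/0.1656 = **0.77**. For ρ from 0.3 to 0.8 the range is 0.73 to 0.77.
- With intake adjustment in both analyses: score variance 0.800 − 0.49 = 0.310; split variance 0.1656 − (0.3989 × 0.7)² = 0.0876. Information kept: 0.159 × 0.310/0.0876 = **0.56**. The range is 0.70 (ρ = 0.3) to 0.45 (ρ = 0.8).
- In the intake-adjusted case, with the plan's 106 per group, 80% power and an assumed two-sided 5% level, the detectable difference on the score is 2.802 × √(2/106 × 0.310) = 0.21 SD. After the split it is 0.214/√0.563 = 0.29 SD.

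The median is the kindest cut. At a single visit, the share kept is 64% with half of participants above the cut, 54% with a quarter, and 34% with a tenth.

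**Step 3. Missing scored as the worst day count.** The 15% missing and the 28-day window are the plan's. The value 28 and the observed mean m are assumed.

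- Rise in a group mean with 15% missing: 0.15 × (28 − m) = 4.2, 3.9 and 3.5 days for m = 0, 2 and 5.
- Two groups with the same m and 10% versus 20% missing: spurious difference 0.10 × (28 − m) = **2.8, 2.6 and 2.3 days**.

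**The case against.** The best reply is that a logit model can be made to work. The 28-day window in 7b already supplies a binomial denominator for diversion, and an ordinal logit can handle scores. On that view, the plan is incompletely specified rather than wrong. The Missing data paragraph also plans a comparison without imputation and calls for tentative conclusions if the two disagree.

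Much of this stands. A reader might infer that logistic regression or an odds ratio is wrong in principle for these outcomes. The documents do not support that, and the fix below keeps a logit for diversion. A worst value could also be imputed; the fault is that none is stated. But 7c does not leave the model open. It asks for models like the yes/no primary model and names no adaptation, and the comparison without imputation supplies neither a variable nor a model form.

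It is also fair that no median split is planned, and that 7c adjusts for stratification covariates only. The 77% is therefore closer to the plan as written, and the 56% applies once intake scores are used.

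A further tempting inference concerns diversion. Section 4a describes the follow-back record of daily dose-taking for participants who report being in buprenorphine treatment. A reader might conclude that people who have left treatment have no diversion data, and that their handling could reverse the group comparison. The documents do not show this. That sentence is about doses taken, while 7b defines diversion for participants without restriction. A buprenorphine-negative urine does not establish that someone has left treatment. A person without medication may truly have no diverted days, so a lower mean across everyone randomised need not be an artefact. What remains is smaller: the plan does not say how diversion is counted for people no longer in treatment.

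**Conclusion.** The concern holds as a mismatch between the stated analysis and the stated outcomes. The binary model cannot be fitted to diversion, overdose risk, SF-36 or CSQ-8 as defined. The SF-36 and ASI-Lite variables are not named. The primary missing-data rule has no stated value for a count or score. These conclusions rest on the text alone.

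The sizes are illustrations. The information figures assume a normal score, a median split and equal correlations. The spurious difference of 2.3 to 2.8 days assumes a worst-value imputation and unequal missingness that the plan does not state.

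The reach is limited to these secondary outcomes and their follow-up. Nothing here bears on the two primary urine outcomes, the 375-participant sample size or the Cox model for retention. It should be fixed, but it does not threaten the main result.

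**What to change.** Settle the following before any group comparison of these outcomes is run.

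In 7c, Statistical Analyses and Secondary outcome analyses:
- Limit the binary logistic GEE to the urine outcomes.
- Diversion: analyse diverted days out of 28 with a grouped-binomial logit GEE and robust standard errors, without dichotomising. The odds ratio then compares the odds that a day in the window is a diverted one.
- Overdose-risk total, named SF-36 score or scores, and named ASI-Lite area scores: use GEE with an identity link, reporting mean differences with 95% confidence intervals, adjusted for the intake score already collected and the stratification covariates.
- CSQ-8: the same, using the intake value only if satisfaction at intake is meaningful.
- An ordinal logit stated in advance would also be acceptable for the scores.

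In 7c, Missing data:
- Confine missing-as-adverse to the binary urine outcomes.
- For counts and scores, name one method valid under missing at random: multiple imputation, or the mixed model the plan already contemplates. Keep the planned comparison without imputation.
- State how diversion is counted for participants no longer in treatment, and report it beside retention.

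The cost is a few sentences and slightly more analysis work with standard software. Score effects become mean differences rather than odds ratios, so secondary results will not all share one scale. Missing at random is itself an assumption. No change to data collection or sample size is needed.
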